9.1.2. Definition of study analysis sets

The following datasets will be defined and used for the analyses:

- The Safety dataset (SAF population) is defined as those patients included in the study, who have received at least one dose of the study treatment.
- The Full Analysis dataset (FAS population) is defined as those patients included in the study, who have received at least one dose of the study treatment, and who have at least one baseline data.
- The **Per Protocol dataset (PP population)** is defined as those patients of the FAS population without any major protocol deviation.

9.1.3. Patients/Subjects disposition

The number and the percentages of patients enrolled and included in each of the populations will be tabulated. The reason for patient exclusions from each of the populations will also be listed. In addition, the number of discontinued patients with their reason for discontinuation will be tabulated.

9.1.4. Demographic and other baseline characteristics

Demographics and other baseline characteristics will be summarized by treatment arm. This analysis will be conducted on the FAS population.

9.1.5. Treatment compliance

Number of injections will be presented on the FAS population.

9.2. Efficacy Analysis

All efficacy analysis will be conducted on both FAS population and PP population except if otherwise specified.

Descriptive statistics will be presented by treatment arm and include:

- Quantitative variables: mean, standard deviation, minimum and maximum, 95% confidence intervals, median and quartiles will be presented when considered relevant. Number of filled and missing values will also be presented.
- Qualitative variables: count, percentage for each modality and 95% confidence intervals when relevant. Number of missing values will also be presented.

Comparison between treatment and placebo will include the following inferential statistics:

- For Time-to-event analyses Kaplan-Meier estimates will be used.
- Categorical variables: the Fisher exact test or Pearson Chi-2 test, as appropriate, will be used to compare rates of categorical variables between the active group and the placebo arm. When stratification or adjustment of the comparisons will be needed, the Cochran-Mantel Haenszel procedure will be used.
- Continuous variables: parametric ANOVA (or non-parametric ANOVA or an appropriate transformation
 of the data if the assumptions for parametric ANOVA are not met) will be used to compare continuous
 variables between the dose group and the placebo arm. When stratification or adjustment of the
 comparisons will be needed, parametric or non-parametric ANCOVA (or data-transformation) will be
 used.

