2.2. Secondary Objectives

The secondary objectives are:

- To evaluate the long-lasting effect of ABX464 on the viral load after treatment stop (i.e. Day 29) using the Time to Viral Rebound versus placebo;
- To compare the effect of ABX464 on viral load (HIV RNA) versus placebo from Day 0 to Viral Rebound;
- To compare the effect of ABX464 on the CD4+ T cell counts versus placebo from Day 0 to Viral Rebound;
- To compare the effect of ABX464 on the CD4+/CD8+ T cells ratio versus placebo from Day 0 to Viral Rebound;
- To evaluate the effect of ABX464 on HIV reservoir (pro-viral DNA in PBMC) versus from Day 0 to Viral Rebound.
- To assess the Pharmacokinetics parameters of ABX464 given on top of darunavir/ritonavir/cobicistat and ABX464.
- To compare miRNA modulations and tropism of HIV versus placebo from Day 0 to Viral Rebound.

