ABX464 up-regulates miRNA in non-infected and infected PBMCs, making of this micro-RNA a potentially useful biomarker for ABX464 treatment monitoring. The miRNA assays will be performed from the remaining plasma collected for viral load determination. No specific blood sample are therefore needed. Determination of miRNA level in plasma will be performed in order to assess treatment effect by comparing before and after treatment. Assays for miRNA determination and tropism test will be conducted by Theradiag, [name], France.

Blood collected in EDTA tubes should be store at room temperature (20-22°C) and processed within 4 hours after collection. Plasma isolation consist in a centrifugation at 500 G during 10 min at room temperature followed by the storage of 900 μ L de plasma in an eppendorf tube at -80°C (or -20°C) until the end of the study. The plasma should be collected from all viral load samples.

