9.4. Determination of Sample Size

The endpoint considered for the sample size calculation is the Time To Viral Rebound defined as the time between treatment stop (i.e. day 29) and viral rebound detection. According to published studies, the expected median Time To Viral Rebound (calculated from treatment stop) is expected to be 7 days in the 'DRV/RTV or COBI + placebo' group while it should be at least 28 days in the 'DRV/RTV or COBI + ABX464 group' in order to continue the clinical development of this new drug.

According to these hypotheses, the corresponding power was calculated using the PROC POWER of the SAS software (version 9.4). Thus, the enrolment of 28 evaluable patients at a dose level (21 in the ABX464 at 50 mg or 150 mg and 7 in the group placebo) will permit to have 80% power to detect a significant difference, at 0.05 level, between groups using the Time To Viral Rebound as end point.

Thus, the overall sample size can vary from 28 patients (in case the dose escalation procedure is not recommended) to 36 patients in case the dose escalation to 150 mg o.d. is recommended.

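### Section 9.2 should fix ANCOVA on the Day 0 value as the method for the continuous secondary markers, instead of defaulting to ANOVA with adjustment left undefined

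*Protocol*

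**What the plan says.** Section 9.2 gives the method for comparing active treatment with placebo as "Continuous variables: parametric ANOVA (or non-parametric ANOVA or an appropriate transformation" of the data if the parametric assumptions fail. Adjustment is conditional: the next sentence begins "When stratification or adjustment of the" and continues "comparisons will be needed, parametric or non-parametric ANCOVA (or data-transformation) will be" used. It does not say when adjustment counts as needed, which covariate would enter, or whether the response is the follow-up value or the change from Day 0.

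The markers concerned are secondary objectives in section 2.2, for example "To compare the effect of ABX464 on the CD4+ T cell counts versus placebo". Similar objectives cover the CD4/CD8 ratio, proviral DNA and miRNA, each from Day 0 to viral rebound.

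Day 0 values exist for all of them. Section 5.2.2 lists CD4/CD8 counts and reservoir blood at Day 0. Section 5.3.5 quantifies HIV-DNA at Day 0. Section 5.3.6 takes miRNA from the plasma of every viral load sample, which includes Day 0. That section says the miRNA level will "assess treatment effect by comparing before and after treatment", and names no model.

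Section 9.4 gives the group sizes per dose level: "21 in the ABX464 at 50 mg or 150 mg and 7 in the group placebo".

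**The concern.** With 7 patients in one arm, the standard error of a between-arm difference is large, and the arms can easily start apart by chance. The patient's own Day 0 value is the obvious covariate and is already collected. A default that omits it can lose precision and leave part of a chance Day 0 difference in the estimate. A switch to ANCOVA without a stated criterion also leaves open which analysis is the planned one.

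What is at stake is the precision and clarity of the secondary marker comparisons.

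**Working it through.** **The plan's own figure.** The only power statement, in section 9.4, is that 28 patients "will permit to have 80% power to detect a significant difference, at 0.05 level, between groups using the Time To Viral Rebound as end point". The placebo median "is expected to be 7 days in the 'DRV/RTV or COBI + placebo' group" and the ABX464 median is at least 28 days, so the hazard ratio under exponential survival is 7/28 = 0.25. With 21 v 7 and two-sided 0.05, a Gehan test with 8 weeks to 3 months of follow-up gives 80.7%. A log-rank test gives 82.4% at 28 days and 85.7% at 3 months. The 80% is therefore reproducible under the Gehan assumption, although the section states neither test nor follow-up. It concerns rebound time only. No power is stated for the continuous markers.

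**Inputs for the markers.** Group sizes 21 and 7 (section 9.4). The correlation r between Day 0 and follow-up is not in the document, so it is an assumption shown over a range. Further assumptions are one follow-up visit with all 28 patients contributing, and the same SD in both arms and at both times.

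**Standard error of the ABX464-minus-placebo difference, in SD units**

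- ANOVA on the follow-up value: sqrt(1/7 + 1/21) = sqrt(0.1905) = 0.436.
- ANOVA on change from Day 0: 0.436 × sqrt(2(1 − r)).
- ANCOVA: 0.436 × sqrt((1 − r²)(1 + 1/24)), where 1/24 is the small-sample price of estimating one slope.

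Example at r = 0.7: the change factor is sqrt(0.6) = 0.775, so the SE is 0.338. The ANCOVA factor is sqrt(0.51 × 1.0417) = sqrt(0.531) = 0.73, so the SE is 0.318.

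| r | SE, follow-up ANOVA | SE, change ANOVA | SE, ANCOVA | ANCOVA / follow-up ANOVA | SE gain over change ANOVA |
|---|---|---|---|---|---|
| 0.3 | 0.436 | 0.516 | 0.425 | 0.97 | about 18% |
| 0.5 | 0.436 | 0.436 | 0.386 | 0.88 | about 12% |
| 0.7 | 0.436 | 0.338 | 0.318 | 0.73 | about 6% |
| 0.8 | 0.436 | 0.276 | 0.267 | 0.61 | about 3% |
| 0.9 | 0.436 | 0.195 | 0.194 | 0.44 | about 0.5% |

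A simulation of 40,000 trials at each of r = 0.5, 0.7, 0.8 and 0.9 agreed with these standard errors to within 0.003.

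**Break-even.** ANCOVA matches ANOVA on the follow-up value when (1 − r²) × 25/24 = 1, so r² = 0.04 and r = 0.2. At r = 0 its variance is 25/24 = 1.04 times as large, a 4% loss.

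**Difference detectable with 80% power** (non-central t, two-sided 0.05, 26 df for ANOVA and 25 for ANCOVA):

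- ANOVA on the follow-up value: 1.27 SD at any r.
- ANOVA on change: 1.27, 0.98, 0.80 and 0.57 SD at r = 0.5, 0.7, 0.8 and 0.9.
- ANCOVA: 1.24, 1.12, 0.93, 0.78 and 0.57 SD at r = 0.3, 0.5, 0.7, 0.8 and 0.9.

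**Chance imbalance.** The difference in Day 0 means also has SE 0.436 SD. The probability that it exceeds 0.5 SD in either direction is 2 × (1 − Φ(0.5/0.436)) = 0.25. A fraction r of it is expected to carry into an unadjusted follow-up comparison. In simulated trials with no true effect where the ABX464 arm started more than 0.5 SD higher, ANOVA on the follow-up value showed an average difference of 0.36, 0.50 and 0.58 SD at r = 0.5, 0.7 and 0.8, while ANCOVA showed about 0. Over all simulated trials the mean ANOVA difference was 0 to within 0.002 SD.

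**The case against.** The best reply is that this belongs to the SAP. Section 9 calls itself a summary and defers technical detail, and section 9.2 already permits ANCOVA. The SAP is not at hand and may name the covariate. What survives is that the protocol is not silent: it states ANOVA as the default and gives the alternative no trigger. Stating the better method costs almost nothing.

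Second, the text never says that ANOVA is run on the raw follow-up value. Objectives framed from Day 0 fit an analysis of change equally well. This stands, and at high r it removes most of the gain. A reader might infer that power for a 0.8 SD difference rises from 42% to 68%, 82% or 98%. That needs both the raw-value reading and an assumed r of 0.7, 0.8 or 0.9, and the document commits to neither. The CD4 entry floor of 600 cells (section 4.2.1) or a direct drug effect on miRNA could lower r.

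Third, a reader might infer that section 5.3.6 abandons the placebo comparison for miRNA. It does not say so. It describes a laboratory procedure, and a before/after change compared between arms would satisfy 5.3.6, 2.2 and 9.2 together. Only the wording needs aligning.

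Fourth, a reader might infer that adjustment will be chosen with unblinded results in view. The document does not support that: the trial is double-blind, no interim analysis is planned (section 9.1), and SAP amendments must be justified and signed before database lock (section 9).

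Finally, these are unpowered secondary markers in a Phase IIa safety study, and the synopsis describes the efficacy endpoints as summarized descriptively. That limits the weight of the point without removing it, since section 9.2 does plan inferential comparisons.

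**Conclusion.** The point holds as an inexpensive improvement to a stated method. Its size cannot be fixed from the document. It ranges from nothing below r of about 0.2, through a standard error about 27% smaller at r = 0.7 if the default means the follow-up value, to a few per cent or less at r of 0.8 and above if it means change from Day 0. ANCOVA is the safer default because it does not require guessing which of those two analyses suits each marker; its worst case against follow-up ANOVA is 4% in variance at r = 0.

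The imbalance argument should be put no higher than this: error given the imbalance that happens to occur, carried over in proportion to r. A reader might take it as bias, or as the whole imbalance entering the estimate; neither is correct, because ANOVA is unbiased over repeated randomizations. The primary safety objective and the 80% power for time to rebound are unaffected.

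**What to change.** In section 9.2, state that the continuous secondary markers (CD4, CD4/CD8, HIV-DNA, miRNA) are compared by ANCOVA with the same marker's Day 0 value as covariate. Use the log10 scale for HIV-DNA and miRNA, with rank ANCOVA as the fallback if the assumptions fail. Report the adjusted ABX464-minus-placebo difference with its 95% confidence interval. Remove the open condition on adjustment for these markers.

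In section 5.3.6, say that the before/after change in miRNA is compared between the ABX464 and placebo arms by that model, as section 2.2 requires.

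The cost is wording and one degree of freedom (25 instead of 26). No extra samples, visits or patients are needed.

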9.2.1. Pharmacokinetics

A total of 22 blood samples per patient will be collected for PK purpose.

Individual plasma concentrations of ABX464, NGIcABX464, DRV, and RTV or COBI will be presented by treatment and time points. Descriptive statistics for the plasma concentrations will be presented as number of available data (N), mean, standard deviation (SD) and will be calculated if at least 2/3 of the plasma values per time-point are above LOQ (i.e. $N \ge 10$ if 15 patients are available for a given group). For descriptive statistics calculations, BLQ concentrations below the limit of quantification will be set to zero (0) if they are reported before the first quantifiable sample or considered as missing data if they are reported after the first quantifiable data.

Then, the following PK parameters will be derived for ABX464, NGIcABX464, DRV, and RTV Day 53 for each patient:

 C_{max} , t_{max} : the maximum plasma concentration (C_{max}) and the time taken to reach C_{max} (t_{max}) will be obtained directly from the concentration-time data.

AUC_{0- τ}: the area under the concentration-time curve from time zero to the time of dosing interval τ (24 h post-dose for ABX464 and NGIcABX464, and 12 h post-dose for DRV and RTV). If no concentration can be measured at this time point, AUC0-last (from time zero to the last quantifiable concentration) will be calculated. Both parameters will be presented independently. For both parameters, a linear trapezoidal method will be used.

Individual derived PK parameters will be presented by treatment and day of PK assessment when appropriate. Descriptive statistics of the PK parameters will be presented as N, mean, SD, coefficient of variation (CV %), median, minimum (Min), maximum (Max) values, and geometric mean (GM).

In the tables of individual PK parameters, all the deviations from planned analysis will be mentioned by flagging the abnormal results.

Possible exclusion of flagged PK parameters could be performed if, in the judgment of the pharmacokineticist, they are deemed not to be "pharmacokinetically relevant". Exclusion of PK parameters will be discussed in the PK results section. If data are excluded from the PK dataset, all subsequent statistical analyses will be performed twice, once using the complete available PK dataset and once using the final PK dataset as defined by the pharmacokineticist. Study conclusion will be based on the final dataset as defined by the pharmacokineticist.

For each compound, plasma concentration vs. time curves will be presented on a log-linear scale:

- mean plots showing the data of both treatments (administration alone and co-administration with ABX464);
- by patient plots with the treatments on separate plots (spaghetti plots).

Formal PK Statistics

It is assumed that all PK data of DRV and RTV/COBI obtained with co-administration of placebo will be gathered in a placebo group accounting for a theoretical total of a minimum of 7 patients.

Evaluation of drug-drug interaction

The relative bioavailability (F_{rel}) after multiple dose administration with either co-administration of ABX464 or of placebo will be evaluated on PK parameters determined on Day 25.

The comparison will be performed on Cmax and AUC_{0-t} using a 1-way ANOVA model with treatment as main effect on logarithmically transformed data. For each parameter, a point estimate for the ratio of geometric means (DRV/RTV or COBI with 50 mg ABX464 / DRV/RTV-COBI with placebo) will be obtained by calculating the difference of least square means on the logarithmic scale and subsequent back transformation with the exponential function. Likewise, 90% confidence interval for the ratios will be obtained by back transforming the 90% confidence intervals of least square mean differences on log-transformed PK parameters.

Moreover, evaluation of steady-state will be made by visual inspection of the pre-dose concentration measurement collected over the study duration.

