	Clinical laboratory parameters, vital signs, ECG will be summarized by using descriptive statistics (n, mean, SD, SEM, median, minimum and maximum). Number of patients with at least one abnormal values will be tabulated (counts and percents) for each parameter in summary shift tables, by group and dose.
	Efficacy: All efficacy endpoints will be summarized descriptively. Time to virological failure, time to treatment failure, HIV reservoirs, etc. will be analyzed by dose versus placebo. Kaplan-Meier estimates will be calculated for these variables (median time to virological failure, viral rebound and estimation of response duration).
	Pharmacokinetics: Considering that DRV/RTV or DRV/COBI is a chronic treatment and that ABX464 is planned to be used as a complement of ART and thus as a chronic treatment too, it is more relevant to determine the possible PK interaction at steady-state.
	 As a result, the t_{1/2} of each drug must be considered to set the optimum days for PK assessment: DRV t_{1/2} is around 15 h, steady-state is expected to be reached after 5 times the t_{1/2} of a given drug, DRV should be reached around 75 h after the first administration, i.e. between the 3rd and the 4th day of administration.
	 RTV has a low t_{1/2} (about 5 h), this means that following a twice daily administration, steady-state could be considered as reached from the second or third day of administration with a negligible drug accumulation.
	 COBI terminal plasma half-life is approximately 3 to 4 h which is slightly lower than ritonavir. Likewise RTV, following a twice daily administration, steady-state of COBI could be considered as reached from the second or third day of administration with a negligible drug accumulation.
	 ABX464 has a very short t_{1/2} (1 to 2 h) and generally no drug could be quantified after 10 h post-dose, so steady-state is virtually reached at the second administration.
	 NGIcABX464 (main ABX464 metabolite) has a t_{1/2} of 90 to 110 h, meaning that steady-state is reached after 19 to 22 days of administration.

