	The drug with the longest $t_{1/2}$ drives the decision, thus blood collection for PK purpose should be done at least 22 days after initiation of ABX464 administration. To prevent individual patient exhibiting slightly slower NGIcABX464 elimination, the PK blood collection will be done on Day 25 +/- 4 days (From Day 21 to Day 28 days after initiation of ABX464 administration). Collection of sparse pre-dose samples from Day 1 to Day 25 will allow to control that NGIcABX464 is at steady-state at the time of PK assessment and to check if steady-state pre-dose levels of DRV and RTV are maintained with co-administration of ABX464.
	PK analysis being done at steady-state, overall drug exposure is expressed through determination of AUC ₀₋₁ (i.e. limited to τ =24 h post-dose for ABX464 and NGIcABX464 and 12 h post-dose for DRV and RTV/COBI).

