3. INVESTIGATIONAL PLAN

3.1. Study design

3.1.1. Design and methodology

This study is a placebo-controlled study aimed at assessing the safety of ABX464 administered at 50 mg o.d. (or potentially at 150 mg o.d.) versus placebo in HIV infected patients who are treated with darunavir + ritonavir (DRV/RTV) or darunavir + cobicistat (DRV/COBI). Eligible patients should be treated with darunavir + ritonavir or darunavir + cobicistat as monotherapy for at least 8 weeks prior to baseline. Patients should be fully suppressed (< 50 copies/mL) for at least 6 months prior to enrolment.

Upon screening visit, eligible patients will continue DRV/RTV or DRV/COBI single regimen given respectively at 800 mg of darunavir with 100 mg of ritonavir or 150 mg of cobicistat once a day with food in the morning.

At Day 0, study drug (ABX464 or its matching placebo) will be added on top of this background therapy for the next 28 days. ABX464 or its matching placebo will be given once a day at the fixed dose of 50 mg (or potentially at 150 mg o.d.).

A 3:1 randomization ratio will be applied meaning that, per treatment block, 3 patients will receive ABX464 on top of DRV/RTV or DRV/COBI and 1 patient will receive placebo on top of DRV/RTV or DRV/COBI.

The original fixed dose (i.e. 50mg o.d.) of the study drug has been selected in November 2015 based on the reassuring safety data accumulated on the 50 mg o.d. and the concentrations in ABX464-N-glucuronide, the active metabolite of ABX464. However, in January 2016, the results of first phase IIa study conducted in treatment-naïve HIV infected patients with high viral load upon enrolment (5,000-500,000 copies/mL) confirmed the antiviral activity of ABX464 at higher doses. A reduction of viral load > 0.5 log was observed in 3/12 patients in the 75 and 100 mg cohorts and 4/6 patients in the 150 mg cohort, demonstrating a dose relationship effect of ABX464.

In case the first 8 patients treated for 28 days at 50mg o.d. in the present study (i.e. two first randomization blocks) do not show a DLT, the study protocol plans to study the 150 mg dose. The DSMB will specifically meet once the first 8 patients have been treated for 28 days in order to recommend, if appropriate, a dose increase to 150mg o.d.

At 150mg, the DSMB will meet every 4 patients in order to review on a regular basis the safety profile of this dose level and to recommend, if appropriate, the continuation of the study.

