Since ABX464 undergoes a high level of biotransformation, ratios between metabolite and parent drug appear to be unchanged across the studied dose range but inter-individual variability prevented from definite conclusions.

Therefore, ABX464 should rather be considered as a pro-drug with regard to its short t1/2. Its metabolite, ABX464NGIc exhibits markedly higher blood concentrations and has a much longer t1/2 which could be of pharmacological interest. Last, dose-exposure relationship appears erratic between 50 and 200 mg but tends to linearity up to 150 mg.

PK Study Design

The main objective of the PK analysis is to evaluate the impact of concomitant administration of ABX464 on DRV and RTV/COBI PK characteristics.

Considering that DRV/RTV or DRV/COBI is a chronic treatment, it is deemed more relevant to evaluate the possible drug-drug interaction at steady-state.

With regard to the relatively short $t_{1/2}$ of DRV (15 h), steady-state is expected to be reached between the 3rd and the 4th day of administration. RTV and COBI have a lower $t_{1/2}$ and thus will not require a longer treatment duration to be at steady-state.

ABX464 was shown to have a very short $t_{1/2}$ (1 to 2 h), so steady-state is virtually reached at the second administration, while NGIcABX464 has a $t_{1/2}$ of 90 to 110 h, meaning that steady-state is reached after 19 to 22 days of administration. Therefore, PK blood collection is planned to be done on Day 25 (25 days after initiation of ABX464 administration). Collection of sparse pre-dose samples from Day 1 o Day 25 will allow to control that NGIcABX464 is at steady-state at the time of PK assessment and to check if steady-state pre-dose levels of DRV and RTV are maintained with co-administration of ABX464.

Since PK analysis is done at steady-state, PK blood sampling will be limited to the higher dosing interval and expression of the extent of exposure of each compound will be determined by AUC_{0-τ} (with τ =24 h for ABX464 and NGIcABX464 and 12 h for DRV and RTV).

A first blood sample (reference) for DRV and RTV/COBI will be collected on the first day of treatment before any drug administration then blood samples will be collected for PK purpose at the following days:

- Day 0 pre DRV/RTV-COBI morning dose*;
- Day 7 pre DRV/ RTV-COBI morning dose;
- Day 14 pre DRV/ RTV-COBI morning dose;
- Day 21 pre DRV/ RTV-COBI morning dose;

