6.9. Prior and Concomitant Medication

6.9.1. Background and allowed concomitant treatment

All Patients must be treated by darunavir/ritonavir or darunavir/cobicistat given as a monotherapy for at least 8 weeks prior to baseline. Ritonavir boosted protease inhibitor treatment should be given at the following doses:

- 800 mg of darunavir and 100 mg of ritonavir once a day with food or
- 800 mg of darunavir and 150 mg of cobicistat once daily with food.

This ritonavir boosted protease inhibitor treatment should be continued during the study period until Day 28.

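### Darunavir and its booster are given once daily, but the dosing-interval AUC for the interaction analysis stops at 12 h

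*Protocol*

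**What the plan says.** **Regimen.** Protocol section 3.1.1 has patients continue "800 mg of darunavir with 100 mg of ritonavir or 150 mg of cobicistat once a day with food in the morning". Section 6.9.1 repeats once-daily dosing for both boosters, for cobicistat as "800 mg of darunavir and 150 mg of cobicistat once daily with food". The synopsis agrees, both under study design and under medications.

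**AUC interval.** Sections 5.3.7 and 9.2.1 define AUC0-τ as the area from time zero to the end of the dosing interval, then fix τ at 24 h for ABX464 and its glucuronide "and 12 h post-dose for DRV and RTV". The PK Study Design text of section 5.3.7 says the same ("and 12 h for DRV and RTV"). The synopsis has "12 h post-dose for DRV and RTV/COBI" and is the only place that gives cobicistat a τ.

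**Twice-daily wording.** The synopsis PK text reasons, for ritonavir, that "following a twice daily administration, steady-state could be considered as reached" within two or three days, and it carries the same premise over to cobicistat. No dosing section supports that premise.

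**Comparison.** Section 9.2.1 states: "The comparison will be performed on Cmax and" an AUC printed as AUC0-t, using a one-way ANOVA on the log scale and a 90% confidence interval for the ratio of geometric means, ABX464 against placebo. Pre-dose samples are taken on Days 0, 7, 14, 21 and 25 "to check if steady-state pre-dose levels of DRV and RTV are maintained with co-administration of ABX464". They are inspected visually and do not enter the ratio analysis.

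**The concern.** At steady state, the AUC over one complete dosing interval equals bioavailable dose divided by clearance. That identity is why AUC0-τ serves as the exposure measure in an interaction analysis. It fails for an AUC cut at half the interval. If ABX464 speeds up or slows down darunavir elimination, the concentrations that move most are the late ones, and those are the ones dropped. The ratio is then pulled towards 1 in either direction, and the result would still be labelled a dosing-interval AUC.

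Section 5.3.7 names the effect of ABX464 on darunavir and its boosters as the main objective of the PK analysis, so this concerns that analysis's principal measure.

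**Working it through.** **1. The stated interval.** τ = 24 h / doses per day. Once daily gives 24 h. The plan's 12 h is reproduced only with two doses per day, which no dosing section states. The 12 h appears in the synopsis, twice in section 5.3.7 and once in section 9.2.1, so it is not a single slip.

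**2. Inputs for the size.**
- From section 5.3.7: darunavir half-life 15 h, tmax 2.5-4.0 h; cobicistat half-life 3-4 h, tmax 3.5 h; ritonavir half-life 3-5 h.
- Assumed: one compartment, first-order absorption, steady state on 24 h dosing. No ritonavir tmax is given, so an absorption rate ka of 0.5-1.5 per h is assumed.
- For darunavir and cobicistat, ka is solved from the stated tmax: 0.58-1.18 per h for darunavir, 0.34-0.43 per h for cobicistat.

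**3. Share of the 24 h AUC captured by 12 h.** With ke = ln 2 / half-life, integrating the steady-state curve gives

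F = AUC0-12 / AUC0-24 = [ka/(1 + e^(−12·ke)) − ke/(1 + e^(−12·ka))] / (ka − ke)

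Darunavir: ke = 0.6931/15 = 0.0462 and e^(−12·ke) = 0.574.
- tmax 2.5 h (ka 1.183): F = (1.183/1.574 − 0.0462)/1.137 = 0.620
- tmax 4.0 h (ka 0.578): F = 0.604

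| Compound | F | Left out by stopping at 12 h |
|---|---|---|
| Darunavir | 0.604-0.620 | 38-40% |
| Cobicistat | 0.817-0.853 | 15-18% |
| Ritonavir (ka assumed) | 0.781-0.931 | 7-22% |

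**4. Effect on the darunavir ratio.** If ABX464 multiplies clearance by m, with volume, absorption rate and bioavailability unchanged, the 24 h ratio is 1/m and the 12 h ratio is (1/m) × F(m·ke)/F(ke). For m = 2 at tmax 2.5 h: 0.5 × 0.731/0.620 = 0.589.

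| Clearance | AUC0-24 ratio | AUC0-12 ratio |
|---|---|---|
| × 0.5 | 2.00 | 1.81-1.83 |
| × 1.25 | 0.80 | 0.84 |
| × 1.5 | 0.67 | 0.72-0.73 |
| × 2 | 0.50 | 0.58-0.59 |

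Read in reverse, an AUC0-12 ratio of 0.80 corresponds to a 24 h ratio of about 0.75-0.76. The protocol sets no expected interaction and no no-effect limits, so these are illustrations only.

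**5. Is the planned sampling enough for 24 h?** The linear trapezoid on the Day 25 times (pre-dose, 0.5, 1, 1.5, 2, 2.5, 3, 3.5, 4, 6, 8, 12 and 24 h) gives ratios of 0.67 for clearance × 1.5 and 0.51 for × 2, against true values of 0.67 and 0.50. It is enough.

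**The case against.** - **The AUC compared may not stop at 12 h.** Section 9.2.1 prints AUC0-t, and the abbreviation list has a separate entry for the area to the last quantifiable concentration. With a 15 h half-life and a 24 h sample, that area would normally reach 24 h. Section 9.2.1 also says that AUC0-τ and AUC0-last will both be presented. This stands as a real ambiguity. However, the synopsis and section 5.3.7 make AUC0-τ the expression of exposure, and section 9.2.1 calculates AUC0-last only when the sample at τ is not measurable. AUC0-τ is therefore the natural reading. On the other reading, the tested measure would differ from the one declared, and the text would still need correcting.
- **The bias depends on the mechanism.** If ABX464 changes only the bioavailable fraction, all concentrations scale alike and the 12 h and 24 h ratios coincide. This is correct. The distortion arises when elimination changes.
- **Small shifts are lost in the noise.** With 21 against 7 patients and an assumed between-patient CV of 20-40%, the 90% interval runs from the ratio divided by about 1.16-1.33 to the ratio multiplied by it. That is wider than the shift from 0.80 to 0.84. This is fair for small interactions, but the shift is systematic, and imprecision does not justify keeping it.
- **The late data are not lost.** The 24 h concentrations are summarised, the curves are plotted and troughs are collected, so a fall late in the interval would be visible. This also stands and limits the severity, but none of it enters the formal ratio.

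**Conclusion.** The concern holds. The 12 h dosing interval contradicts the protocol's own once-daily regimen in every section that sets τ, and the twice-daily wording in the synopsis contradicts the dosing sections. That conclusion needs no model.

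The size does rest on a model: one compartment, the protocol's half-lives and tmax values, and a change in clearance alone. On that basis the 12 h AUC omits 38-40% of darunavir's daily exposure and draws the interaction ratio towards 1. The shift is modest for a small interaction (0.84 for 0.80) and material for a large one (0.58-0.59 for 0.50). It applies if the AUC compared in section 9.2.1 is AUC0-τ, which is the natural but not the only reading.

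This should be fixed. It is not critical, because pharmacokinetics is a secondary objective and the exposure can be recomputed from samples already planned.

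**What to change.** - Reconcile the once-daily dosing statements with the twice-daily reasoning in the synopsis. Which schedule applies is for the sponsor to confirm.
- Under the once-daily regimen as written, set the analysis interval τ to 24 h for darunavir, ritonavir and cobicistat in the synopsis, section 5.3.7 (both places) and section 9.2.1, naming cobicistat each time.
- State in the drug-drug interaction paragraph of section 9.2.1 that this AUC0-τ is the AUC compared.
- Optionally, add the 24 h concentration to the ratio analysis.
- A separate slip in the same section: it derives the PK parameters on Day 53, while section 5.3.7 and the interaction paragraph use Day 25. Make these agree.

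The cost is wording only. The 24 h sample on Day 25 is already scheduled, so no visit or blood draw is added.
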